9.0 STATISTICAL CONSIDERATIONS

9.1 Definition of primary outcome/endpoint

9.1.1 Pilot Portion: Occurrence of Dose Limiting Toxicities (DLTs) between the time of glyburide initiation and the time of the one month follow-up MRI.

9.1.2 Randomized Portion:

Each eligible patient will be evaluated for treatment outcome as success or failure, as defined later in this section. Each patient's treatment outcome will be associated with randomized regimen regardless of the treatment the patient actually receives. A treatment failure will be considered to have occurred if edema increases sufficiently to require the initiation of dexamethasone (or any corticosteroid administration with the purpose of treating cerebral edema) between the time of SRS* and the time of the one month follow-up MRI, or the patient dies in that same interval from a cause considered probably or likely related to Glyburide. Otherwise, the patient will be considered to have experienced treatment success.

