2.0 OBJECTIVES AND ENDPOINTS

2.1 Primary Objectives

2.1.1 Pilot Portion: To determine the feasibility and safety of administering oral glyburide to non-diabetic patients receiving stereotactic radiosurgery (SRS) for newly diagnosed brain metastases.

2.1.2 Randomized Portion: To determine the number of patients with newly diagnosed brain metastases who have an increase in edema as measured on volumetric FLAIR imaging and the number of patients that require dexamethasone administration (or any corticosteroid administration with the purpose of treating cerebral edema) from the day of SRS* to one month follow-up MRI in the group receiving glyburide versus placebo.

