2.3 Primary Endpoints

2.3.1 Pilot Portion: Occurrence of Dose Limiting Toxicities (DLTs) between the time of glyburide initiation and the time of the one month follow-up MRI.

2.3.2 Randomized Portion: Occurrence of edema increase and initiation of dexamethasone (or any corticosteroid administration with the purpose of treating cerebral edema) between the time of SRS* and the time of the one month follow-up MRI.

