8.2 Non-Permitted Supportive Therapy

- 8.2.1** Corticosteroids: Dexamethasone (or any other corticosteroid whose purpose is to treat cerebral edema) should only be administered if the patient is clinically symptomatic, has imaging demonstrating increasing cerebral edema, and is deemed by the treating physician to require dexamethasone (or another corticosteroid). If administered between SRS and the one month follow-up MRI, these patients will be recorded as a treatment failure (primary endpoint). If initiated prior to SRS, this is criteria for withdrawal from the protocol, these patients would be deemed inevaluable. If initiated after the one month follow-up MRI, the dose, value, and reason will be recorded. Low dose prednisone or other non-dexamethasone steroids are allowed as long as they are not administered with the intent of treating cerebral edema.

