8.3 Imaging

- 8.3.1** All patients must have a contrast enhanced MRI within 60 days of study entry.
- 8.3.2** Pre-treatment tumor/edema ratio should be determined by importing the pretreatment MRI into the Eclipse treatment planning system. MRI with and without contrast.T1-weighted, T2 and/or FLAIR MRI of the brain (maximum slice thickness 5mm). FLAIR imaging is preferred. The total volume of tumor and total volume of edema should be recorded. If the ratio of edema/tumor volume is $\geq 35:1$, this will be counted as a risk factor for entering the trial on the Randomized Portion.
- 8.3.3** MRI obtained at the time of SRS (for treatment planning; may be within 21 prior to SRS treatment for patients being treated with linac-based radiosurgery where it is not standard of care to complete a MRI on the day of SRS [as it is with gamma knife]), at the time of the one month follow-up visit, and at the time of the 3 month follow-up visit must be taken with a MRI machine. These studies must all employ MRI with and without contrast. T1-weighted, T2 and/or FLAIR MRI of the brain (maximum slice thickness 5mm). FLAIR imaging is preferred.
- 8.3.4** FLAIR sequences at time of SRS (see note above regarding linac-based radiosurgery patients), one month follow-up, and 3 month follow-up MRI scans will be imported into the Eclipse treatment planning system where FLAIR volume will be automatically calculated using "Region Growing" on Eclipse (Appendix I). The automated contours will be verified and modified as needed by the radiation oncologist. Physicians, patients, and the study team will be blinded to the patient's investigational medication on the Randomized Portion. The primary endpoint of the Randomized Portion will constitute a mean of the edema values as measured by the region growing tool and verified and modified as needed by the radiation oncologist (see Appendix I).

8.3.5 T1 post gadolinium sequences at time of SRS (see note above regarding linac-based radiosurgery patients), one month follow-up, and 3 month follow-up MRI scans will be imported into the Eclipse treatment planning system where the enhancing tumor(s) that was treated with the full dose of SRS will be manually contoured by the radiation oncologist who will be blinded to patient's investigational medication on the Randomized Portion.

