8.4 Definition of Edema Volume

- 8.4.1** Absolute edema volume will be calculated by subtracting the tumor volume as contoured on the T1 post gadolinium sequences (see Section 8.3.5) from the FLAIR edema volume (see Section 8.3.4).
- 8.4.2** Absolute edema will be independently verified and modified as needed by the radiation oncologist.
- 8.4.3** Absolute edema ≤ 1.00 cc will not be considered edema (defined as no edema).
- 8.4.4** Patients will be considered to have edema increase if an absolute edema increase is $\geq 5.0\%$ (this is an absolute percentage) from the time of SRS (see note above regarding linac-based radiosurgery patients) to the time of the one month follow-up MRI.
- 8.4.5** Patients with no edema at time of SRS (see note above regarding linac-based radiosurgery patients) who achieve an absolute edema value of > 1.00 cc at the time of the one month follow-up MRI will be considered to have an edema increase.
- 8.4.6** Primary endpoint of the Randomized Portion is edema increase as defined in Sections 8.4.4 and 8.4.5.

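### The randomized primary endpoint is stated in conflicting ways (MRI edema increase in 8.4.6, steroid-requiring edema or glyburide-related death in 9.1.2), and the 50% placebo success rate is not tied to either

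*Combined protocol and SAP*

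**What the plan says.** All references are to the combined protocol and SAP, randomized portion.

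- **9.1.2** (primary outcome): "A treatment failure will be considered to have occurred if edema increases sufficiently to require the initiation of dexamethasone" or another corticosteroid for cerebral edema between SRS and the one-month MRI, "or the patient dies in that same interval from a cause considered probably or likely related to Glyburide". Then: "Otherwise, the patient will be considered to have experienced treatment success".
- **9.3.2** compares treatment successes by a one-sided exact test, 20 patients per arm. A p-value of 0.30 or less sends glyburide forward. Treatment success is defined only in 9.1.2.
- **8.4.6**: "Primary endpoint of the Randomized Portion is edema increase as defined in Sections 8.4.4 and 8.4.5". Those two sections are purely radiographic: a rise of at least 5.0%, or new edema above 1.00 cc, at the one-month MRI.
- **8.2.1**, on steroids for edema: "If administered between SRS and the one month follow-up MRI, these patients will be recorded as a treatment failure (primary endpoint").
- **2.1.2** counts patients "who have an increase in edema as measured on volumetric FLAIR imaging and the number of patients that require dexamethasone administration", so it lists two counts.
- **2.3.2**: "Occurrence of edema increase and initiation of dexamethasone (or any corticosteroid administration with the purpose of treating cerebral edema"), one phrase joined by *and*.
- **8.3.4**: "The primary endpoint of the Randomized Portion will constitute a mean of the edema values as measured by the region growing tool".
- **9.2.2** lists steroid initiation (item 1) and the mean rate of FLAIR edema increase (item 4) as secondary. The yes/no MRI increase of 8.4.4/8.4.5 is not listed.
- **9.5.2** sets placebo success at 50%, citing the retrospective series described in 1.8, and gives 0.80 power if glyburide success is 75%. It does not say which failure definition the 50% describes.

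**The concern.** Two sections each claim to define the primary endpoint, and they classify the same patient differently. A patient whose edema grows on MRI but who has no symptoms and gets no steroid fails under 8.4.6 and succeeds under 9.1.2. In the other direction, a patient who starts a steroid after SRS fails under 9.1.2 but may show no increase at one month. 9.5.2 itself says that steroid use probably reduced the number of increases seen in the historical series.

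An analyst working from section 9 would use 9.1.2. The MRI count that 2.1.2 and 8.4.6 call primary would then never enter the only decision test. If the conflict is still open when results are known, the definition can be chosen after the fact.

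The sample size has a related gap: a placebo success rate means something only for a stated definition of success.

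**Working it through.** **Inputs.** 20 per arm, one-sided, threshold 0.30 (9.3.2); 50% against 75% success, power 0.80 (9.5.2); 35% volumetric increase with two or more risk factors (1.8). The exact test is taken to be Fisher's, since 9.3.2 does not name it.

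**1. Reproduce the stated power.** For *a* glyburide and *b* placebo successes, with T = a + b,

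p(a, b) = Σ over k ≥ a of C(20, k)·C(20, T − k) / C(40, T).

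Power = Σ over all (a, b) with p ≤ 0.30 of Bin(a; 20, p_G)·Bin(b; 20, p_P).

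With p_P = 0.50 and p_G = 0.75 this gives **0.802**, so the 0.80 reproduces.

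**2. Can the definition reverse the decision?** The counts below are invented to show what is possible, and assume no glyburide-related deaths. Successes are 20 minus failures.

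| Data set | Definition | Failures, glyburide vs placebo | Successes | p | Decision |
|---|---|---|---|---|---|
| A | 8.4.6 (MRI) | 5 vs 10 | 15 vs 10 | 0.095 | go |
| A | 9.1.2 (steroid) | 3 vs 3 | 17 vs 17 | 0.669 | no-go |
| B | 8.4.6 (MRI) | 10 vs 10 | 10 vs 10 | 0.624 | no-go |
| B | 9.1.2 (steroid) | 1 vs 4 | 19 vs 16 | 0.171 | go |

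It can, in both directions.

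**3. What does the 50% describe?** The only rate in the documents for patients with two or more risk factors is the 35% in 1.8, that is 100 − 35 = 65% without an increase. That is an MRI outcome. It is a rough guide only:

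- The follow-up MRI in that series could be as late as 100 days after SRS, against one month here.
- The risk factors differ: melanoma or renal histology there, smoking history in 3.1.9.1.
- Each variable in the 1.8 table sums to 114 (for example 9 + 15 + 14 + 76), although the series had 55 patients.

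9.5.2 argues that steroids hid some increases in that series. This points below 65%, but 50% is not derived from it. No rate of starting steroids is given anywhere, so the documents offer no figure for placebo success under 9.1.2.

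**4. Sensitivity of power.** The planned effect, 50% to 75%, is both a 25-point gain and a halving of failures (50% to 25%). At other placebo rates the two separate:

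| Placebo success | 25-point gain kept | Failures halved (assumption) |
|---|---|---|
| 50% (9.5.2) | 75%: 0.802 | 75%: 0.802 |
| 60% (assumed) | 85%: 0.823 | 80%: 0.704 |
| 65% (from 1.8) | 90%: 0.842 | 82.5%: 0.645 |

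For the last cell, failures of 35% halve to 17.5%, so success is 82.5%.

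**The case against.** The strongest reply is that section 9 governs. Section 9.1 is the one place that sets out to define the primary outcome, and 9.3.2 relies on its term, so the test can be run without guessing. Since 8.2.1 ties steroids to symptoms together with imaging evidence of increasing edema, 2.3.2, 8.2.1 and 9.1.2 can all be read as edema increase that leads to a steroid. On that reading 8.4.6 and 8.3.4 are the outliers, and 2.1.2 needs only clarification. The mean in 8.3.4 may also be a per-patient measurement rule rather than an endpoint.

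Much of this stands. The analysis is executable, and a reader might infer that a composite of MRI increase or steroid start is the only way to reconcile the text. It is not; keeping 9.1.2 is a legitimate choice. But no passage says that 9.1.2 overrides 8.4.6, and on this reading an outcome named as primary in two places still drops out of the decision.

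A reader might also infer that the trial is badly underpowered. The documents do not support that. Keeping the protocol's own 25-point gain, power stays above 0.80 at 60% and 65% placebo success. Rates of 80% or 90% under a steroid-only definition are conceivable, but nothing in the documents supplies them.

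**Conclusion.** The concern holds as an inconsistency that must be resolved before unblinding. The primary endpoint has conflicting definitions, the choice between 8.4.6 and 9.1.2 can reverse the go/no-go decision, and following section 9 leaves the binary MRI increase out of the test.

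The power arithmetic is sound for 50% against 75%. What is missing is the link between that 50% and a definition. At 65% placebo success, power is 0.842 or 0.645 depending on the effect assumed. Under a steroid-based definition it is unknown, because no placebo rate is given.

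Three stronger conclusions do not follow. Opposite decisions are not shown to be likely, since the counts in data sets A and B are illustrative. The 50% is not shown to be wrong: it is not derived in the plan, and the source it cites is not part of these documents. The screening purpose and the liberal 0.30 threshold are not at fault; they affect how strong the evidence must be, not which outcome is counted.

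The figures assume Fisher's exact test, which the reproduced 0.802 supports, and no glyburide-related deaths in the examples.

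**What to change.** Before unblinding, the sponsor should name one primary endpoint and use it in 2.1.2, 2.3.2, 8.2.1 (endpoint label only), 8.3.4, 8.4.6 and 9.1.2.

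- **Option 1, composite.** Failure is any of: edema increase per 8.4.4/8.4.5 at the one-month MRI; start of a corticosteroid for cerebral edema between SRS and that MRI; or the death component already in 9.1.2. Both counts of 2.1.2 then stay in the test.
- **Option 2, keep 9.1.2.** Correct 8.4.6, 8.3.4 and 2.1.2 to match, and add the binary MRI increase by arm as a named secondary endpoint, since 9.2.2 item 4 has only a mean rate.

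Under either option, 9.5.2 should justify the placebo success rate for the chosen definition and restate power at that rate. If MRI enters the test, the plan must say how a missing one-month MRI is handled, so that it does not become a success through the residual clause of 9.1.2. Counting it as failure adds noise; excluding it can bias the comparison if missingness differs by arm.

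The criteria for giving steroids do not change, and all components are already collected. The cost is wording, plus a power figure that may be less favourable than 0.80.

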9.2 Definition of secondary outcomes/endpoints

9.2.1 Pilot Portion

1. Time until dexamethasone initiation (or any corticosteroid administration with the purpose of treating cerebral edema) as measured between the time of SRS* and the time of the one and three month post SRS MRI scans.
2. Incidence of CTCAE version 4.0 reportable toxicities of grades 2-5.

3. Incidence of CTCAE version 4.0 reportable toxicities of grades 1-2 Cardiac Disorders or Hepatobiliary Disorders.
4. Cerebral edema increase as measured on FLAIR volumetric imaging, defined from MRI taken at the time of SRS* and the time of the one and three month post SRS MRI scans.
5. Absolute volume change of index tumor(s) that received radiosurgery as manually contoured by the radiation oncologist defined from T1 post gadolinium sequences at the time of SRS* and the time of the one and three month post SRS MRI scans.

9.2.2 Randomized Portion

1. Dexamethasone initiation (or any corticosteroid administration with the purpose of treating cerebral edema) between the treatment groups (as measured between the time of SRS* and the time of the one and three month post SRS MRI scans).
2. Rate of CTCAE version 4.0 grade 2-5 Nervous system disorder toxicities between the treatment groups.
3. Rate of CTCAE version 4.0 grade 1-5 Cardiac Disorders and Hepatobiliary Disorders between the treatment groups.
4. Comparison of mean rate of cerebral edema increase as measured on FLAIR volumetric imaging between the treatment groups (defined from MRI taken at the time of SRS* and the time of the one and three month post SRS MRI scans).
5. Comparison of median absolute volume change of index tumor(s) that received radiosurgery as manually contoured by the radiation oncologist between the treatment groups (defined from T1 post gadolinium image at the time of SRS* and the time of the one and three month post SRS MRI scans).

* Please note that the MRI may be performed within 21 days prior to SRS treatment only if the patient is being treated with linac-based radiosurgery and it is not standard of care to complete a MRI on the day of SRS (as it is with gamma knife).

9.3 Analytic plan for primary objective

9.3.1 Pilot Portion: Each evaluable patient will be assessed for “*concerning toxicities*” and “*serious toxicities*”. If 6 or more patients demonstrate a “*concerning toxicity*” or 1 or more patients experience a “*serious toxicity*”, the therapy will be considered not feasible to deliver and one dose reduction will occur. If 6 or more patients demonstrate a “*concerning toxicity*” or 1 or more patients experience a “*serious toxicity*” on the dose reduced schedule, the intervention will be considered too toxic and the protocol will be terminated. Inevaluable patients will be replaced.

9.3.2 Randomized Portion:

After the acceptable glyburide dose has been established, the randomized portion will commence. No formal interim monitoring will take place and study analysis will be done when all 20 randomized patients are accrued in each treatment regimen. The results from this portion of the trial will be used as a screening mechanism for assessing whether glyburide should be studied in a formal randomized trial. The number of patients who experience treatment successes will be compared between the two regimens using the

exact test of proportions. If this test yields a one-sided test of equality of proportions of treatment success obtains a p-value of 0.30 or less, glyburide treatment will be considered as sufficiently interesting for further study. Otherwise, glyburide will be considered not interesting for further development. We acknowledge that the type 1 error rate of 0.30 is liberal, and note that this was chosen based on the preliminary efficacy aspect of the study; post-analysis power calculations may be performed.

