T1 post-gadolinium sequences and FLAIR axial sequences from the treatment planning MRI (see note above regarding linac-based radiosurgery patients) and at the one and three month follow-up appointments will be imported into the Eclipse treatment planning system. On the T1 post gadolinium sequences, the radiation oncologist will contour the enhancing tumor that received the prescribed dose of SRS. Using the FLAIR sequences Eclipse will automatically calculate FLAIR volume using “Region Growing” (Appendix I). The automated contours will be verified and modified as needed by the radiation oncologist. Physicians, patients, and the study team will be blinded to the patient’s investigational medication.

5.2.1 Patients can only be enrolled after all eligibility criteria are met. The date of registration/enrollment/study entry is considered to be the day the Eligibility Checklist is signed by the verifying physician and should be no later than 5-9 days prior to SRS. Once a patient is enrolled, a unique case number will be assigned to the patient and blinded randomization will occur. Patients will be randomized by the UAB Investigational Drug Services (IDS) Pharmacy, who will hold the blind for this study.

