group, who will not be allowed to receive steroids unless they experience a clinical failure. As noted above, this selection design will use a type I error rate of 30%. A type I error rate of 30% is used because given the expected accrual in combination with limited funding available for the study, our goal is to determine if there is a signal for treatment success that would generate sufficient interest to escalate the study idea into a cooperative group setting, where the question of efficacy may be more definitively addressed. If the treatment success rate with glyburide is 75%, glyburide will be identified for further study with probability of 0.80. The power associated with other values for the treatment success probability for Glyburide is demonstrated in the figure below:

We project an inevaluability rate of at most 20%. The study will be completed with the enrollment of approximately 63 patients over an estimated 2 year enrollment period after approval.

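### The only analysis in 9.3.2 is tied to completion of accrual, with no condition that the last patients have finished the one-month primary window or the three-month scan

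*Combined protocol and SAP*

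**What the plan says.** Section 9.3.2 rules out interim looks ("No formal interim monitoring will take place") and, in the same sentence, times the single analysis: "study analysis will be done when all 20 randomized patients are accrued in each treatment regimen". Accrual is the only condition given.

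Section 9.1.2 defines treatment failure over an interval. The failure events, steroid initiation for edema or a glyburide-related death, are counted "between the time of SRS* and the time of the one month follow-up MRI, or the patient dies in that same interval". It opens with "Each eligible patient will be evaluated for treatment outcome as success or failure, as defined later in this section" and closes with "Otherwise, the patient will be considered to have experienced treatment success". The imaging definition in 8.4.4 and 8.4.5 ends at the same one-month scan, so the timing question does not depend on which statement of the primary endpoint is used. Secondary endpoint 1 in 9.2.2 is taken "as measured between the time of SRS* and the time of the one and three month post SRS MRI scans", and the edema and tumor volume endpoints there use the same two scans.

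Under 5.2.1 registration "should be no later than 5-9 days prior to SRS". Sections 4.2.7 and 4.2.8 and Appendix VIII place the one-month visit at day 30 (-5 to +10) and the three-month visit at day 90 (-10 to +14) after SRS. Section 5.2 sets the randomized portion at 40 evaluable patients, with inevaluable patients replaced.

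**The concern.** Accrual and outcome are separated by weeks. A patient registered last has not yet had SRS, and the interval that decides success or failure ends at a scan a month after SRS. Followed to the letter, 9.3.2 analyses the trial while the most recent patients have no primary outcome, and while a larger group has no three-month scan.

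The count in the trigger is also not the count the trial is sized on. Steroid use before SRS (4.2.9.2), a DLT before SRS (7.2.3) or failure to proceed to SRS (6.1) makes a patient inevaluable, so evaluability is not known at accrual. Twenty randomized per arm need not be twenty evaluable per arm.

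At stake is a single go/no-go test on 40 patients. A few outcomes that are undefined, or filled in by a default, cost some power and can change the decision in an individual trial.

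**Working it through.** **1. Reproduce the plan's power.** Inputs from 9.3.2 and 9.5.2: 20 per arm, success 50% on placebo and 75% on glyburide, exact test, one-sided p ≤ 0.30. Sum Bin(a; 20, 0.75) × Bin(b; 20, 0.50) over all success counts (a, b) whose one-sided Fisher p-value is ≤ 0.30. Result: power 0.802, matching the stated 0.80. At 50% versus 50% the same sum gives an actual type I error of 0.215.

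**2. Reproduce the enrollment figure.** (10 + 40) / (1 − 0.20) = 62.5, rounded up to 63, matching 9.5.2.

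**3. Time from registration to each endpoint.** Taking registration 5-9 days before SRS:
- One-month MRI: 5 + 25 = 30 days to 9 + 40 = 49 days.
- Three-month MRI: 5 + 80 = 85 days to 9 + 104 = 113 days.

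Earlier registration is allowed, which would lengthen these intervals.

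**4. Patients with open windows at the trigger.** The documents give no accrual rate for the randomized portion. Assume uniform accrual of 50 evaluable to 63 enrolled patients over 24 months: 50/24 = 2.08 to 63/24 = 2.63 per month. Pending patients = rate × days / 30.4.

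| Endpoint | 2.08 per month | 2.63 per month |
|---|---|---|
| One-month MRI (30-49 days) | 2.1-3.4 | 2.6-4.2 |
| Three-month MRI (85-113 days) | 5.8-7.7 | 7.3-9.8 |

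That is about 2-4 of 40 for the primary window and about 6-10 of 40 for the three-month scan.

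**5. Effect on the primary test if open windows were counted as successes.** The plan states no such rule, so this is a conditional calculation. Fix m pending patients as successes, distribute them at random between two arms of 20 (hypergeometric), and repeat the enumeration in step 1 for the rest. It assumes no failure has yet been seen in any pending patient, which makes it an upper limit on the effect of this scoring for each m.

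| Pending (m) | Power, 75% vs 50% | Type I error, 50% vs 50% |
|---|---|---|
| 0 | 0.802 | 0.215 |
| 2 | 0.780 | 0.215 |
| 3 | 0.769 | 0.214 |
| 4 | 0.757 | 0.214 |

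The average loss is about 2 to 4.5 percentage points of power, and average type I error does not rise. With m = 3, simulation puts the share of trials whose go/no-go decision differs from that with complete follow-up at about 8%.

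**6. Randomized versus evaluable.** At the 20% ceiling on inevaluability in 9.5.2, 40 randomized patients would yield about 40 × 0.80 = 32 evaluable. Section 5.2 replaces inevaluable patients, so the two sections give different stopping counts unless the trigger is reworded.

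**The case against.** The sentence in 9.3.2 can be read as contrasting interim looks with one final analysis, not as setting a data cutoff. Section 4.2 schedules one- and three-month visits for every patient, and a comparison of treatment successes needs assessed outcomes, so a sensible analyst would wait. That is a fair account of the probable intent. But the clause on interim monitoring already stands on its own, the second clause says when the analysis is done, and no other passage supplies the missing condition.

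Several stronger readings are tempting, and the documents do not support them:
- *That 9.1.2 itself scores unfinished windows as successes.* It has no rule for them. Its catch-all clause completes a success/failure split for an interval ending at the one-month MRI. Applying it to an interval still open is an inference.
- *That 9.5.2 confirms an early cutoff.* The statement "The study will be completed with the enrollment of approximately 63 patients over an estimated 2 year enrollment period after approval" follows the inevaluability allowance and gives an enrollment total.
- *That the blind would be broken while patients are still on drug.* No passage breaks the blind at accrual. Sections 7.4 and 7.6 restrict unblinding, and 4.2 and 8.3 require blinded contouring.
- *That error rates could be badly distorted.* With 3 pending patients all in one arm, the false-go rate would be 0.09 (all placebo) or 0.37 (all glyburide). Each split has about an 11.5% chance, and the average stays at 0.214.

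Two further points reduce the size. If the count is of evaluable patients and evaluability is settled at SRS, the pending interval is 25-40 days, or about 1.7-2.7 patients at 2.08 per month. And 9.4 makes the secondary analyses largely graphical and descriptive, so missing three-month scans affect no decision rule.

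**Conclusion.** The timing defect holds on the wording: the only stated trigger precedes the close of the primary window for the last patients, and it counts a different population from 5.2. How open windows would be classified is left unsaid. The consequence for the primary test is modest. Power falls from 0.80 to about 0.76-0.78 if 2-4 open windows were counted as successes, without average type I inflation. The three-month summaries would lack about 6-10 of 40 patients.

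These sizes rest on uniform accrual over 24 months with pilot and randomized portions pooled, on registration 5-9 days before SRS, and, for power, on a scoring rule the plan does not state. If some failures among pending patients are already recorded, the loss is smaller. The case for changing the text is that a stated rule misfires when followed and correcting it costs little.

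**What to change.** Replace the trigger in 9.3.2 with wording to this effect: the primary analysis is done after the last of the 40 evaluable patients has completed the one-month MRI, or its window (day 40 after SRS) has closed; the three-month endpoints are analysed after the last three-month window (day 104 after SRS) has closed. Use evaluable, as in 5.2, in place of randomized in that sentence. Add to 9.1.2 that no patient is classed as a success before the one-month window has closed.

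Cost: the primary analysis falls about 1-1.6 months after last accrual (30/30.4 to 49/30.4), and the three-month analyses about 3-4 months after (85/30.4 = 2.8 to 113/30.4 = 3.7). No visits are added, and the target of 40 evaluable patients is unchanged.
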